Transcoronary Infusion of Cardiac Progenitor Cells in Pediatric Dilated Cardiomyopathy December 9, 2020

Study design and outcome measures

The clinical study was registered as NCT03129568 (ClinicalTrials.gov). The TICAP-DCM (Transcoronary Infusion of Cardiac Progenitor Cells in Pediatric Dilated Cardiomyopathy) phase 1, open-label trial was conducted at Okayama University Hospital between July 24th, 2017, and September 17th, 2018. The study design and protocol were approved by the Ethics Committee of Okayama University (01F1701003) and followed the Guidelines on Clinical Research Using Human Stem Cells issued by the Ministry of Health, Labour and Welfare, Japan. This trial was performed in accordance with the Declaration of Helsinki with written consent from all parents of eligible patients.

Children aged less than 18 years with a diagnosis of DCM based on clinical and echocardiographic findings were screened and the study enrollment required evidence of LV dilation with reduced EF defined as less than 40% (*1*). Although neuromuscular, mitochondrial, syndromic, and metabolic causes were considered to be further validated by genetic screening, sarcomeric mutation analysis was not performed in patients with cardiomyopathy with either isolated or LVNC phenotype. Exclusion criteria included cardiogenic shock, intractable arrhythmias, repeated infections, advanced renal or hepatic dysfunction, and manifested cancer diseases. Mixed hypertrophic or restrictive cardiomyopathy phenotypes were also excluded. Every eligible participant was subjected to endomyocardial biopsies to obtain sufficient specimens for pathological diagnosis and CDC culture. Patients classified as secondary DCM, such as inflammation, toxic exposure, metabolic disorders, and structural heart disease, were not enrolled in this trial.

The TICAP-DCM prospective, open-label, phase 1 trial comprised of a phase 1a study (n=5, prespecified as 7 but limited to 5 patients available for recruitment due to the disease severity and rarity) to evaluate procedural safety during intracoronary delivery of CDCs $(3.0 \times 10^5/\text{kg})$ using nonocclusive approach, and a phase 1b study (n=24, in a 1:1 randomization) to assess the therapeutic benefits. The sample size was determined based on a power of 85% to detect a difference of 4.5% in the cardiac function, assuming that the common standard deviation is 3.5% between controls and CDC-treated groups using a 2-group t test at 2-sided. Study participants were assessed at baseline, 6, and 12 months of follow-up. The primary safety endpoint was adverse events occurring in the treatment arm including ventricular fibrillation, ventricular tachycardia, heart failure, myocardial infarction, advanced infection, and tumor formation after CDC infusion (2). The secondary endpoint was to assess the functional improvement of the global cardiac function and heart failure status from baseline to 6 months of follow-up, as described previously (3). The study participants were closely monitored by an independent data monitoring committee at the Center for Innovative Clinical Medicine. Data management board at Translational Research Center for Medical Innovation (Kobe) has verified and vouched for the accuracy, completeness, and fidelity of the clinical data.

Statistical analysis

Descriptive data are presented as absolute numbers and percentages or means and SDs. Significance of differences between two treatment groups was assessed using Student's *t*-test. Paired *t*-test was used to determine the significance between baseline and an endpoint within a group. For multiple comparisons of continuous measures between groups, the Kruskal-Wallis test was used if normality could not be established. When the variables were distributed normally, one-way analysis of variance (ANOVA) was performed and Tukey post hoc test was applied to determine the statistical significance between groups. Categorical variables presented by the number of observations between the groups were compared using Fisher exact test. Individual comparisons at baseline to 6 and 12 months of follow-up were analyzed by one-way ANOVA with repeated measures followed by Dunn–Bonferroni post hoc correction according to the data normality. The Friedman test was used to analyze the heart failure status in CDCtreated patients from baseline to 12 months of follow-up and Wilcoxon signed-rank test with Dunn–Bonferroni post hoc correction was applied to compare the changes from baseline. Linear regression analysis using Pearson's correlation coefficient was applied to evaluate the relationship between absolute changes in the extent of myocardial fibrosis from baseline to 12 months of follow up and the expressions of CDCex-derived miRNAs, and *r* values were presented as Pearson product-moment correlation coefficient. A *P* value less than 0.05 was considered to be significant. Analyses were conducted using SPSS software (version 26, IBM Corporation, Armonk, NY).

- S. E. Lipshultz, Y. M. Law, A. Asante-Korang, E. D. Austin, A. I. Dipchand, M. D. Everitt, D. T. Hsu, K. Y. Lin, J. F. Price, J. D. Wilkinson, S. D. Colan, Y. American Heart Association Council on Cardiovascular Disease in the, C. Council on Clinical, G. Council on, M. Precision, Cardiomyopathy in Children: Classification and Diagnosis: A Scientific Statement From the American Heart Association. *Circulation*, CIR000000000000682 (2019).

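### The primary safety endpoint covers only the treatment arm and is timed only as after infusion, so it omits control-arm biopsy harm and leaves in-procedure and other biopsy events undecided

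*Combined protocol and SAP*

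**What the plan says.** All the design statements are in the combined protocol and SAP under Study design and outcome measures.

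- **Phase 1a:** its purpose is "to evaluate procedural safety during intracoronary delivery of CDCs". Its size is given as "a phase 1a study (n=5, prespecified as 7 but limited to 5 patients available for recruitment".
- **Phase 1b:** "a phase 1b study (n=24, in a 1:1 randomization) to assess the therapeutic benefits".
- **Primary safety endpoint:** "The primary safety endpoint was adverse events occurring in the treatment arm including ventricular fibrillation, ventricular tachycardia, heart failure", and the list then closes with "heart failure, myocardial infarction, advanced infection, and tumor formation after CDC infusion". The sentence cites an earlier phase 1 trial report by the same programme.
- **Biopsy:** "Every eligible participant was subjected to endomyocardial biopsies to obtain sufficient specimens for pathological diagnosis and CDC culture".
- **Assessment times:** "Study participants were assessed at baseline, 6, and 12 months of follow-up".

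The only other endpoint is the secondary one, on cardiac function and heart failure status. No start or end of safety observation is stated. No biopsy or catheter complication is named. The Statistical analysis section sets out no safety-specific analysis or interval, although it provides Fisher's exact test for categorical comparisons between groups.

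**The concern.** A safety endpoint needs a population, a list of events and a time window. Here the population is one arm, the list is open, and the window is a single phrase at the end of the list.

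Three things are at stake.

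1. All participants were exposed to biopsy, but the endpoint looks only at treated patients. The risk of the whole strategy (biopsy, catheterisation and cells) cannot be read from it.
2. The phase 1a question concerns the delivery procedure itself. If the closing phrase governs the whole list, that period is left out.
3. With no control-arm count in the endpoint, heart failure and arrhythmia in treated children, which can arise from the underlying disease, have no comparator.

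The trial was open-label. An endpoint that supports two readings lets the reading be chosen after events are known.

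**Working it through.** **The plan's own figure.** The section's one computed figure is the phase 1b size of 24. With a difference of 4.5, an SD of 3.5, two-sided alpha 0.05 (taken from the Statistical analysis section) and 12 per arm, the t test has 85.3% power, which matches the stated 85%. That calculation concerns cardiac function and has no bearing on safety. The plan gives no figure for the safety endpoint.

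**Which events count.** Reading A lets the phrase about infusion govern the whole list. Reading B attaches it only to tumor formation and treats the list as open.

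| Event | Reading A | Reading B |
|---|---|---|
| Biopsy harm, phase 1b control | Not counted | Not counted |
| Biopsy harm, treatment arm, later infused | Not counted | Could count; not named |
| Biopsy harm, treatment arm, never infused | Not counted | Unclear |
| VF, VT or MI during infusion | Not counted | Counted |
| Other catheter complication during infusion | Not counted | Could count; not named |
| Heart failure or arrhythmia in a control | Not counted | Not counted |
| Listed event after infusion, treatment arm | Counted | Counted |

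Biopsy must precede infusion because the infused cells are cultured from the biopsy tissue. The first and sixth rows do not depend on the reading, because the restriction to the treatment arm decides them.

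**How many participants are affected on any reading.** Phase 1b controls: 24 / 2 = 12. If phase 1a and phase 1b patients are distinct (an assumption), participants total 5 + 24 = 29, and 12/29 = 41% of those biopsied are outside the endpoint.

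**What one event does in phase 1a (illustrative).** Exact Clopper-Pearson limits, n = 5:

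- 0/5: the lower limit is 0. The upper limit is 1 - 0.025^(1/5) = 0.52, so the interval is 0-52%.
- 1/5: the lower limit is 1 - 0.975^(1/5) = 0.005. The upper limit solves (1-p)^5 + 5p(1-p)^4 = 0.025, giving p = 0.72. The estimate is 20%, with interval 0.5-72%.

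**How often the question would arise.** The documents give no event rates, so the rates below are assumed. The chance of at least one event is 1 - (1-p)^n.

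| Assumed true rate p | In-procedure event, n = 5 | Biopsy event among controls, n = 12 |
|---|---|---|
| 5% | 23% | 46% |
| 10% | 41% | 72% |
| 20% | 67% | 93% |

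**The case against.** The strongest reply is that the sentence has been read too narrowly. The word *including* leaves the list open, and the phrase about infusion sits beside tumor formation and may modify that item alone. Even if it governs the list, *after* could mean from infusion onward. Ventricular fibrillation, ventricular tachycardia and myocardial infarction are named, and all could occur during an intracoronary infusion. Since the same paragraph gives phase 1a a procedural purpose, it is natural to suppose that delivery events count. This stands. A reader might infer that the endpoint counts only post-infusion events and so cannot answer the phase 1a question. The documents do not support that; they show an ambiguity on the point.

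Second, the phase 1a purpose concerns delivery and not biopsy, and the biopsy also served diagnosis. This stands too. The biopsy gap is an omission from the safety endpoint, not a contradiction of the phase 1a objective.

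Third, the cited earlier trial report may define the window. It may, but it is not available here, and the plan's own text should carry the definition of its primary endpoint.

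Fourth, an independent data monitoring committee watched participants closely. That makes it less likely that harm went unseen, but it does not decide what the primary endpoint counts.

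None of these replies reaches the treatment-arm restriction. It is stated outright, and it excludes control-arm biopsy harm and any comparator however the timing phrase is read.

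**Conclusion.** The concern holds in two layers.

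- **On any reading:** the primary safety endpoint omits biopsy harm in the 12 phase 1b controls and has no comparator. This assumes that the statement about biopsy in every eligible participant includes controls, as it says.
- **On the literal reading only:** it also omits biopsy harm in treated patients, whether or not they were later infused, and events during infusion. Because the list is open, the documents do not settle whether this reading was intended.

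A reader might also infer that the strategy's risk was in fact understated. The documents report no biopsy or procedural event and no rate, so that cannot be said. The n = 5 intervals and the assumed-rate table show only how much one classification decision could matter in a group this small.

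This should be corrected, because it changes what the trial can conclude about safety. It does not affect the sample size or the efficacy analysis.

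**What to change.** State in the endpoint definition that:

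1. safety observation starts at the endomyocardial biopsy for every participant in both arms, including anyone biopsied but never infused, and when it ends;
2. events during the procedure count.

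Tabulate the listed events, plus biopsy and catheter complications, in three periods: biopsy to infusion, during infusion, and after infusion. Give exact 95% intervals. Show control-arm counts alongside over the matching periods before and after allocation. Keep phase 1a and phase 1b separate so that the procedural result for the first group can be seen.

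**Cost.** A change of wording and one more table; reported event rates may rise. The document is dated December 2020 and the trial ran from July 2017 to September 2018, so the change applies to analysis and reporting and should be labelled as a clarification made after the trial was conducted. It is an assumption that biopsy and in-procedure events were recorded in both arms. The documents describe monitoring by a committee and data verification, but do not say that these events were captured. If they were not, the report should say so and limit its safety statement to the periods actually observed.

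### The repeated-measures ANOVA and Friedman test drop any child who lacks one of the three visits, and no rule covers missing data, death or transplant, so the secondary efficacy results risk survivor bias.

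*Combined protocol and SAP*

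**What the plan says.** The Study design and outcome measures section sets assessments at baseline, 6 and 12 months. It places the secondary endpoint (global cardiac function and heart failure status) at baseline to 6 months, and the primary endpoint is adverse events in the treatment arm. Phase 1b randomises 24 children 1:1. Its size rests on this: "The sample size was determined based on a power of 85% to detect a difference of 4.5% in the cardiac function". The other stated inputs are an SD of 3.5%, taken as equal in both arms, and a two-sided t-test for two groups.

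The Statistical analysis section names these tests:

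- Student's t-test between two treatment groups.
- A paired t-test within a group, from baseline to one endpoint visit.
- For the three-visit comparison: "Individual comparisons at baseline to 6 and 12 months of follow-up were analyzed by one-way ANOVA with repeated measures", with a post hoc correction.
- The Friedman test for heart failure status from baseline to 12 months, in treated patients only, with signed-rank comparisons from baseline.

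On software it says: "Analyses were conducted using SPSS software".

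Neither section defines an analysis set, a missing-data method, a rule for outcomes after death or transplant, a sensitivity analysis or a dropout allowance.

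**The concern.** Classical repeated-measures ANOVA and the Friedman test work on complete rows. A child without a 12-month value leaves the whole analysis, and the 6-month value goes too. The plan can therefore discard valid data at its own efficacy visit because of something that happened later.

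The second issue is who leaves. Children enter with an ejection fraction (EF) below 40%, and heart failure and ventricular arrhythmia are among the listed adverse events. Loss through deterioration is plausible. If the children who do worst have no follow-up value, the remaining mean change is too favourable and a within-arm test may read this as functional improvement. Phase 1b exists to assess therapeutic benefit, so this bears on its main efficacy message.

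**Working it through.** **Inputs.** From Study design and outcome measures: difference 4.5, SD 3.5, power 85%, two-sided two-group t-test, 12 per arm. From Statistical analysis: alpha 0.05 ("value less than 0.05 was considered to be significant"). Assumed, because the documents do not give them: an SD of within-patient change of 3.5, and every loss rate below.

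**1. The plan's own figure.** Noncentrality = 4.5 / (3.5 × √(2/12)) = 3.15 on 22 degrees of freedom. Exact power is 85.3%, so 24 is reproduced with no allowance for loss. With 11, 10 or 9 evaluable per arm, power is 81.8%, 77.6% or 72.6%.

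**2. Which test needs which visits.**

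| Test | Visits needed | Child seen at 6 months, missing at 12 |
|---|---|---|
| Two-group t-test at 6 months | 6 months (with baseline, if change is analysed) | kept |
| Paired t-test, baseline to 6 months | baseline, 6 | kept |
| Signed-rank test, baseline to 6 months, run on its own pair | baseline, 6 | kept |
| Repeated-measures ANOVA | baseline, 6, 12 | dropped |
| Friedman test | baseline, 6, 12 | dropped |

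If a share m is missing independently at each follow-up visit, 12 × (1 − m)² children per arm remain in the three-visit tests. For m = 5% this is 12 × 0.9025 = 10.8; for m = 15% it is 12 × 0.7225 = 8.7. This measures lost precision, not bias.

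**3. Shift in the arm mean, no true effect.** If the lowest k of 12 changes are lost, the shift is 3.5 × (−sum of the k lowest expected normal order statistics) / (12 − k). The three lowest order statistics for n = 12 are −1.629, −1.116 and −0.793.

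- k = 1: 3.5 × 1.629 / 11 = 0.52
- k = 2: 3.5 × 2.745 / 10 = 0.96
- k = 3: 3.5 × 3.538 / 9 = 1.38

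Against the target of 4.5 these are 12%, 21% and 31%. If loss follows a factor correlated r with the outcome, the shift is multiplied by r. At r = 0.5 it is 0.26, 0.48 and 0.69; at r = 0 it is zero.

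**4. False findings (simulated null trials, nominal 2.5% in the favourable direction).**

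| Scenario | 1 lost | 2 lost | 3 lost |
|---|---|---|---|
| Within-arm improvement, worst lost | 9% | 18% | 30% |
| Within-arm improvement, r = 0.5 | 4% | 6% | 8% |
| Between-arm cell-therapy win, worst lost from treated arm only | 6% | 11% | 16% |
| Same, worst lost from both arms | 3.5% | 4.5% | 5.0% |
| Same, worst lost from control arm only | 1.3% | 0.7% | 0.4% |

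Losing the worst two from one arm moves the between-arm difference by about +1.0 (treated arm only), −1.0 (control only) or 0 (both).

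**5. Phase 1a.** Losing the worst 1 of 5 shifts the mean by 3.5 × 1.163 / 4 = 1.0 point.

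**The case against.** The main efficacy comparison may be untouched. The size is built on a two-group t-test, and differences between treatment groups are assigned to Student's t-test. At 6 months that test does not need the 12-month value, and nor does the paired t-test. This stands: the listwise loss of 6-month data belongs to the three-visit tests only, and the plan does not name either of them as the between-arm efficacy test.

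A reader might infer that the efficacy result is biased towards survivors, or that it favours the cell therapy between arms. The documents support neither reading. They report no death, transplant or missed visit, and they nowhere state that complete cases are used; that follows from the tests named when nothing else is specified. Bias requires loss that is related to outcome. The between-arm direction depends on which arm loses more, and heavier loss among controls would work against the cell therapy. The remark that phase 1a was "limited to 5 patients available for recruitment due to the disease severity and rarity" explains recruitment, not loss to follow-up. The exclusion of cardiogenic shock, intractable arrhythmia and advanced organ dysfunction removes some of the children most likely to be lost early.

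Removing exactly the worst children is also an extreme case, so its figures are upper bounds.

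None of this removes the gap. The three-visit tests still discard usable endpoint data, and no rule says how a child without a 6-month value enters any of the tests.

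**Conclusion.** The point holds as a conditional risk to the secondary efficacy endpoint. Two things are certain from the named methods: the repeated-measures ANOVA and the Friedman test exclude children with an incomplete series, and nothing in the plan overrides this. The rest depends on loss being related to outcome, on the assumed SD of change of 3.5 and on the assumed number lost. Under those assumptions the within-arm mean change is too favourable by about 0.3 to 0.7 points at a correlation of 0.5, and by at most about 0.5 to 1.4 points, for 1 to 3 losses from 12. The direction is clear only within an arm. The primary safety endpoint is adverse events and is not shown to use these tests. If no child missed a visit, reporting the number analysed at each visit settles the matter.

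**What to change.** **Phase 1b.** Replace the repeated-measures ANOVA with a likelihood-based mixed model for repeated measures on all available visits of all randomised children. Take baseline, 6 and 12 months as responses, with arm, visit and arm-by-visit terms and small-sample degrees of freedom. Name the 6-month arm contrast as the efficacy result. This recovers 6-month data that listwise deletion discards.

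The model alone is not enough. A child with no follow-up value adds almost nothing to it, and it does not handle outcomes truncated by death or transplant. Add a between-arm rank test at 6 months that ranks those children worst, as a sensitivity analysis. Report these events, and the number analysed, by arm and visit.

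**Heart failure status.** State the number in the Friedman test, and base the signed-rank comparison at 6 months on all children with both values.

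**Phase 1a.** An arm-by-visit model does not apply to five children in a single arm. Report individual values and the number analysed at each visit.

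**Cost.** Revised analysis wording, a standard mixed-model procedure in the software already named and slightly more analysis work. The rank result is not expressed in EF points.

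### The only analysis that names heart failure status omits the randomised controls and is not labelled descriptive; no between-arm 6-month test is tied to this endpoint component

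*Combined protocol and SAP*

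**What the plan says.** The section on study design and outcome measures describes "a phase 1a study (n=5, prespecified as 7 but limited to 5 patients available for recruitment" and, separately, "a phase 1b study (n=24, in a 1:1 randomization) to assess the therapeutic benefits". The secondary endpoint is "to assess the functional improvement of the global cardiac function and heart failure status from baseline to 6 months of follow-up". On visits it states: "Study participants were assessed at baseline, 6, and 12 months of follow-up", with no restriction by arm.

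The Statistical analysis section mentions heart failure status in one sentence: "The Friedman test was used to analyze the heart failure status in CDCtreated patients from baseline to 12 months of follow-up". The same sentence adds a Wilcoxon signed-rank test, for which Dunn–Bonferroni "post hoc correction was applied to compare the changes from baseline".

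That section also gives general between-group rules. "Significance of differences between two treatment groups was assessed using" Student's t-test, and "Categorical variables presented by the number of observations between the groups were compared using Fisher exact test". Neither rule is linked to heart failure status or to the 6-month visit. A single threshold of P below 0.05 applies to all tests, and no test is called descriptive or supportive.

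**The concern.** A Friedman test and a signed-rank test ask whether patients in one group changed over time. They cannot say whether any change is due to the cells or would have happened anyway through natural course or background care. The controls in phase 1b were randomised to answer that second question, yet the one analysis assigned to this component does not use them.

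Where a specific rule stands beside general ones, a reader will take the specific rule as the planned analysis. An improvement shared by both arms could then be reported as significant for an efficacy component.

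The time point is not the difficulty. The Friedman test runs to 12 months, but the signed-rank step can include the 6-month contrast.

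The population is also unclear. CDC-treated patients could mean the 12 randomised to cells, those 12 plus the 5 from phase 1a (17), or the 5 alone.

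**Working it through.** **The plan's own figure.** The sample size rests on cardiac function: difference 4.5%, SD 3.5%, two-sided t test, power 85%. Taking alpha as 0.05 from the general rule, 12 per arm gives exact t-test power of 85.3% (11 per arm: 81.8%), so 24 reproduces. It was set for a comparison of treated patients with controls, and it says nothing about power for heart failure status.

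**Worked example, with no assumed rates.** Take any ordered class scale and 12 treated patients. Suppose m improve one class by 6 months and hold it to 12 months, and none worsen.

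- Friedman, three visits, tie-corrected. The rank sums are 24 + m at baseline and 24 − m/2 at each later visit. The uncorrected statistic is [12/(12·3·4)] × 1.5m² = 0.125m². The tie correction factor is m/16. The statistic is therefore 2m on 2 degrees of freedom, and P = exp(−m).
- Signed-rank at 6 months, large-sample form. All m non-zero changes are tied and favourable, so z = √m. The exact two-sided P is 2 × (1/2)^m.
- Bonferroni multiplies the signed-rank P by 2, for 6 and 12 months against baseline.

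| m of 12 | Friedman P | Signed-rank P (×2) | Exact signed-rank P (×2) |
|---|---|---|---|
| 5 | 0.0067 | 0.0253 (0.051) | 0.0625 (0.125) |
| 6 | 0.0025 | 0.0143 (0.029) | 0.0312 (0.0625) |
| 7 | 0.0009 | 0.0082 (0.016) | 0.0156 (0.031) |

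Six improvers are enough with the large-sample P, and seven with the exact P. No control result enters any of these numbers.

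Now compare 6 of 12 treated with the controls, using an exact rank-sum test. With changes of one class or none, this is the same as Fisher's test.

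| Controls improving | 0/12 | 1/12 | 2/12 | 3/12 | 6/12 |
|---|---|---|---|---|---|
| Between-arm P | 0.014 | 0.069 | 0.193 | 0.400 | 1.0 |

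The treated-only result is significant in all five columns. The between-arm result is significant only in the first.

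**How often this could happen with no treatment effect.** This part rests on assumptions that are not in the documents: a four-class scale, baseline classes II/III/IV at 30/50/20%, improvement in months 6–12 at half the first-period rate, and 5% worsening per period. The full procedure is Friedman P < 0.05 plus a favourable signed-rank P < 0.025. Each figure comes from 10,000 simulated trials.

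| Improving by 6 months | 5% | 10% | 20% | 30% | 40% |
|---|---|---|---|---|---|
| n=12, at 6 months | 0% | 0.1% | 1% | 9% | 23% |
| n=12, at 6 or 12 months | 0% | 0.2% | 5% | 20% | 42% |
| n=12, at 6 months, exact signed-rank | 0% | 0% | 0.3% | 3% | 11% |
| n=12, at 6 or 12 months, exact signed-rank | 0% | 0% | 1.5% | 9% | 26% |
| n=17, at 6 or 12 months | 0% | 1% | 15% | 42% | 70% |

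Under no worsening, 5% or 10% worsening and three baseline class splits, the n=12 figures at 6 or 12 months (large-sample P) range over 3–9%, 12–36% and 26–66% at 20%, 30% and 40% improving. With n=5 the procedure is never significant: even if all five improve one class, the corrected P is 2 × 0.0253 = 0.051. Under the same assumptions, the exact between-arm test at 6 months rejects in at most 2.3% of trials.

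**The case against.** The strongest reply is that the plan already has a between-arm rule. If each patient either improves one class or does not, the plan's Fisher test gives exactly the between-arm P values shown above. The Statistical analysis section is a list of general rules that does not assign a test by name to cardiac function or to the safety endpoint either, and it labels no test descriptive. The endpoint sentence does not say that the comparison is against control. If CDC-treated patients means the five in phase 1a, there are no controls to leave out. The simulated rates are not error rates of the named test, since its null of no change is false when patients improve. They also rest on assumed inputs and are low at 6 months unless spontaneous improvement is common.

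Much of this is fair. The plan is not without a between-group test, the rates are conditional, and they mislead only if a treatment effect is claimed from them. Three things remain:

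- Heart failure status does have a specific rule, and that rule is treated-only. The text does not define the scale, so it does not settle whether a t-test or Fisher's test would apply.
- The between-arm reading is an inference, but a strong one: phase 1b is randomised, its stated purpose is benefit, and its sample size compares two groups.
- On the five-patient reading, phase 1b has only the unassigned general rules for this component, so the gap remains.

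**Conclusion.** The concern holds. The one analysis assigned to heart failure status cannot support a conclusion about treatment effect, and nothing in the plan prevents its P value from being read that way. The case is mainly structural: the treated-only P value is the same whether none or half of the controls improve, while the between-arm P moves from 0.014 to 1.0.

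How often this would mislead depends on spontaneous improvement, which the documents do not give. Under the assumptions above, with 12 patients and large-sample P values, the chance of a favourable result with no treatment effect clearly exceeds 5% only from about 25–30% improving. It is lower with exact P values and higher if phase 1a is pooled. This should be fixed, but it concerns a secondary component of a phase 1 trial whose primary endpoint is safety.

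**What to change.** - For phase 1b as randomised, name one between-arm comparison of change in heart failure status from baseline to 6 months as the inferential analysis. State the scale and choose a test that suits it, for example an exact Wilcoxon rank-sum test if it is ordinal.
- Label the Friedman and signed-rank results for heart failure status descriptive, with no claim of benefit resting on them.
- State which patients are meant by CDC-treated, and report phase 1a patients separately.

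The cost is SAP wording and one named test. The scheduled baseline and 6-month assessments supply the data. The within-arm P values lose inferential status.

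The between-arm test has limited power at 12 per arm. Treating improvement as yes or no, with assumed rates, exact power is about 39% for 20% versus 60%, 64% for 10% versus 60%, and 21% for 30% versus 60%. A non-significant result should therefore be called inconclusive. The text is in the past tense, so if outcomes have already been seen, the added test should be labelled as specified afterwards.
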